5.5.2.2 Mechanistic measures (baseline only)

The mechanistic measures of determinants of response to therapy (Fig.2) will be acquired at baseline (T0) only, and include for all participants the NIHSS, a perception-grasping dissociation task (5min), the visual field VISA sub-test (5min), the OCS (15min), the Gesture Recognition sub-test of the BCoS (5 min), the (optional) CENT (5min) and the stroke lesion location (extracted from clinical scans and reports). For those who are able and consent to MRI we will also acquire a multimodal neuroimaging protocol (30min) measuring structural and functional IPS connectivity.

- **NIHSS** will be extracted from participants medical files and used as measure of stroke severity as recommended [31].
- The **perception-grasping dissociation task** (5min) consists of asking patients to either point to centre of a rod or reach for the rod using a pincer grip, as if to lift the rod so it would be balanced. [19-20, 80]. The rods are placed on a mat with their

centre shifted into the patient's affected hemispace. The deviation from the centre is recorded by therapist in eCRF. The task was adapted from studies showing that neglect is reduced when participants reach to grasp the centre of rods to balance them compared with when they point to the perceived centre [19-20, 80]. We hypothesize that patients who present smaller dissociations between the two tasks may benefit less from SIGHT.

- The **VISA visual field sub-test** (5min) is an 'aphasia friendly' and stroke validated measure of visual field deficits (e.g., hemianopia quadrantanopia) [44]. It involves a 5-minute test, where an examiner moves a target inward from the visual field peripheries to determine visual field deficits, finger counting in each visual field quadrant and a qualitative response from the patient of whether the sides of the examiner's face are seen equally e.g. is one side of the face more blurred.
- The OCS is an established quick (15min) cognitive screen consisting of 10 tasks encompassing five cognitive domains: attention and executive function, language, memory, number processing, and praxis [45]. The OCS was devised to be inclusive and un-confounded by aphasia and neglect. The OCS offers advantages over other screening tools in terms of ease of completion and feasibility for stroke survivors with physical, language or visuospatial impairments [69]. Moreover, the OCS is more sensitive than the Mini Mental State Examination at detecting cognitive deficits poststroke [70] and assesses stroke-specific cognitive deficits not assessed by the Montreal Cognitive Assessment or the Addenbrookes Cognitive Examination [71].
- The gesture recognition sub-test of the BCoS (5min) will be used to provide quick and valid way to detect apraxia using procedures designed to be inclusive for patients with aphasia and/or spatial neglect [76]. Participants will view familiar gestures (object and non-object related) and asked to choose their meaning. As we are recruiting both right, left and bilateral hemisphere strokes this will help examine whether those with apraxia in our sample are able to benefit from SIGHT.
- **CENT** (5min) is a sensitive computerised 'aphasia friendly' measure of neglect of far space (or extrapersonal neglect) that has been validated in stroke and shown to predict stroke recovery and ADL deficits [77,87]. Participants are asked to use a mouse to click on targets on a screen. The scores are automatically generated.
- The clinical brain imaging scans (CT and/or MRI) and their reports will be extracted and used to map the stroke lesion location. Lesions will be manually delineated by UEA team on the structural scan using open-source cross-platform medical image viewers such as MRICROn 72]. Then, the checked lesion maps will be normalized to stereotaxic space using the age-specific template within the Statistical Parametric Mapping Software (SPM) clinical toolbox developed for stroke lesion-symptom mapping studies [73]. Routine clinical brain scans have been demonstrated to be of sufficient quality for lesion mapping research [74-75] and will ensure that lesion mapping can be performed for the full sample (N=206), instead of only those who complete the MRI (N=80), giving us sufficient power (minimum recommended N=100 [75]) for determining the lesion locations significantly associated with lower therapy response.
- Mechanistic neuroimaging MRI measures will be acquired at sites who are participating in this sub-study and will cover structural, diffusion and functional brain imaging. Patients who consent and have no MRI-contraindications will be transported to the 3T MRI facility within the hospital they are in. The entire neuroimaging protocol

will be completed within approximately 30min, but 1hr has been allocated to allow patient positioning and removal from the scanner which can take longer in disabled patients. Earplugs and cushions will be provided for comfort. Patients will be given a squeeze emergency ball in their spared hand to alt the scanning and asked to relax while keeping their head still. Head motion will be monitored throughout data acquisition and feedback provided as necessary via the intercom. The neuroimaging modalities selected are feasible in stroke survivors with neglect [28-30] and are recommended for inclusion in stroke trials [31]. Their combination will provide the richest and largest neuroimaging dataset in neglect post-stroke (leading samples published in separate studies to date: structural MRI=68 [53]; structural DTI=38 [54]; rsfMRI=25 [28]). The neuroimaging mechanistic measures will include a series of scan sequences:

- T1-weighted whole brain scan for alignment to normalised space of remaining neuroimaging data (7min). The scan will be a 3D scan with resolution of 1x1x1 mm3 and provide good WM/GM contrast
- T2 FLAIR (5min). The scan will have a resolution of approximately 1x1x3 mm3, it should provide good lesion contrast.
- Diffusion weighted imaging scan (DWIDTI; 8min) for white matter tractography. The sequence should have approximately 60 gradient directions and 3-5 b=0 scans, resolution should be approximately 2x2x2 mm3. It is likely to require some form of parallel imaging to meet the timing requirements. The plan is to do a single shell of b=1000 s/mm2, however if all sites are able then a multi-shell sequence with a second, larger, b-value will be considered.
- Resting-state functional MRI (rsfMRI; 10min) to measure changes in blood oxygenation associated with intrinsic brain activity (i.e., in the absence of an explicit task or stimulus). Again, the resolution should be approximately 2x2x2 mm2, with approximately 250-300 volumes.

Anonymised neuroimaging data will be sent to UEA research team via the Image Exchange Portal and processed using specialist software such as SPM and FSL. We will use well-established pre-processing routines for motion-correction, coregistration, smoothing and temporal filtering, and standardised pipelines that facilitate comparisons across studies (e.g., fMRIprep). Regions of interest (ROIs) will be manually identified in each participant in left and right IPS (seed regions) by visual inspection of the T1 using established anatomical landmarks and then centring a sphere closest to the peak coordinates associated with neglect improvement [28]. ROIs overlapping with lesion will be excluded from analysis.

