superior fronto-occipital fasciculus (SFO), is also relevant as it is significantly associated with severity of both egocentric and allocentric neglect [54]. In addition, resting-state functional magnetic resonance imaging (rsfMRI) studies in neglect have repeatedly shown that the connectivity of the structurally intact IPS to other brain regions within the damaged hemisphere seems key [28-30;58]. Specifically, interhemispheric (left-right) functional connectivity between the IPS and the rest of the brain is the most robust correlate of neglect deficits at 2 weeks post-stroke (r=0.55; p<0.001, N=25 neglect patients [28]). In fact, interhemispheric (left-right) functional connectivity between the IPS and the rest of the IPS and the rest of the brain even predicts neglect improvement at 12-weeks post-stroke (r=0.58; p<0.001, N=25 neglect patients [28]).

Thus, the mechanistic study embedded into the proposed efficacy trial aims to test if both behavioural and neuroimaging measures can be used as determinants of therapy response (Fig.2). Our testable hypothesis, based on the neuroimaging studies reviewed above, is that neglect patients with structural or functional damage to IPS and/or its projections will benefit less from SIGHT [16]. Notably, it is important to acknowledge, as highlighted above, that the neglect syndrome does not occur in isolation, but is often accompanied by other post-stroke visual and cognitive deficits (e.g., hemianopia and executive functioning) which also further impede stroke recovery and functional outcome [57]. Thus, to carefully examine the impact of these factors, our mechanistic study will combine innovative neuroscience and clinical expertise to characterize each patient's residual IPS structure and function, perception-grasping dissociation, cognitive and visual profile and stroke severity, and test if these measures can determine response to SIGHT, following MRC and American Society of Neurorehabilitation guidelines [31-33].

[figure not shown]

Figure 2. Mechanistic study of determinants of response to therapy.

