4.2 Objectives

This multicentre RCT aims to investigate the clinical efficacy of SIGHT on post-stroke neglect when delivered by a therapist in tightly controlled within-hospital settings, whilst simultaneously determining the causes of differing responses to therapy between individuals. Our primary research aims are to:

(1) determine whether SIGHT in addition to TAU produces greater reduction in neglect than TAU alone (i.e., standard occupational therapy for neglect).

(2) determine whether benefits from SIGHT are still evident at the 12-week follow-up after the intervention ends.

(3) determine if therapy response is modified by: (a) lesion location; (b) left and right IPS functional connectivity; (c) left and right IPS structural connectivity; (d) perception-grasping dissociation; (e) stroke severity, (f) visual and/or (g) cognitive deficits.

Our testable hypotheses, generated by our early phase work and neuroimaging studies [16,19-20,26-27], are that:

(1) when added to treatment as usual (TAU), 30 minutes/day of SIGHT for 7 days (over a 10-day period) will produce greater reduction in neglect than TAU alone.

(2) patients with impaired IPS structure or function will benefit less from SIGHT.

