
Regarding the mechanistic brain imaging, a sample of 40 per group, which includes 20% attrition, will provide greater than 90% power at 2.5% level of significance (as we have 2 correlations the significance level is adjusted) to detect a correlation of 0.58 between IPS structure and function and treatment response in each arm separately. This sample size is directly informed by published data showing that interhemispheric (left-right) functional

connectivity between the IPS and the rest of the brain predicts neglect improvement at 12weeks post-stroke (r=0.58; p<0.001, N=25 neglect patients [28]). Importantly, the total sample size of 80 for the brain imaging study is feasible within our timeframe based on the FAST-Indicate EME stroke trial [55] and the published rates of 45% for MRI attrition in acute stroke [61]. Specifically, we expect that approximately 112 of the 206 recruited participants will be able and consent to undergo MRI and thus our sample size of 80 is achievable.

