The evaluation of mechanistic determinants of response to therapy will be modelled using a general linear model using the following baseline data: structural connectivity as per fractional anisotropy of fibres connecting IPS seed-regions and defined areas in the rest of the brain; inter-hemispheric (left-right) functional connectivity as per time course correlations between IPS seed-regions and rest of the brain; perception-grasping score computed from difference in deviation from rod centre between grasping and perception; stroke severity; visual field VISA sub-test score; and, OCS domain scores. To determine if treatment effect is modified by these mechanistic variables, we will correlate change scores (from baseline to T1, i.e. therapy response; Fig.2) and each of these measures while regressing out lesion volume (computed from the lesion map) as lesion size correlates with stroke recovery [28]. Each data will be included separately and then data reduction methods will be applied so that all the measures can be included in a single model. The study investigating IPS will test effects in each arm separately as well as test for an interaction to see if the association is different in the two arms. In addition, to determine if lesion location predicts treatment response (hypothesis 2), we will use lesion-symptom mapping analysis and test if specific lesion sites are associated with smaller change scores/therapy response.

If patients receive less than 70% of the intervention, they will be included in the intention-totreat efficacy analysis and T1 and T2 measures will still be collected and included in the mechanistic analysis to predict overall neglect recovery. An additional per-protocol analysis will be conducted in which these individuals will be excluded so that we can differentiate the effect of being allocated to the intervention (the intention-to-treat analysis) and the effect of the intervention if the participant, and therapist, adhere (the per-protocol analysis).

Site will be used as strata for the randomisation; this should remove any potential confounding for TAU variation across sites. In the analysis we will report the 'dose' given to the participants. We will carry out a per-protocol analysis including individuals who have received an appropriate dose of SIGHT (>70%). In the intervention group, we will correlate the amount of therapy received against the change in the primary outcome measure.

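### Side-specific IPS measures are labelled left and right while right, left and bilateral strokes are pooled without a stroke-side term, so each mixes ipsilesional with contralesional values

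*Protocol*

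**What the plan says.** Objective 3 (Protocol 4.2) lists among the possible modifiers of response "b) left and right IPS functional connectivity; (c) left and right IPS structural connectivity". Section 5.5.2.2 places the seeds accordingly: "Regions of interest (ROIs) will be manually identified in each participant in left and right IPS (seed regions"). It also says that seeds overlapping the lesion are dropped. The same section, on the gesture recognition test, describes the intake: "As we are recruiting both right, left and bilateral hemisphere strokes".

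Section 5.10.4.1 gives two IPS predictors. The structural one is fractional anisotropy (FA) of fibres between the IPS seeds and other areas. The functional one is called inter-hemispheric (left-right), but is then described as time-course correlations between the seeds and the rest of the brain. Change scores are correlated with each measure "while regressing out lesion volume (computed from the lesion map"). No other covariate is named for these correlations.

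The background (4.1) says that "connectivity of the structurally intact IPS to other brain regions within the damaged hemisphere seems key", and then names inter-hemispheric connectivity as the strongest correlate of the deficit.

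Section 5.7 describes the target effect for the imaging study as being able "to detect a correlation of 0.58 between IPS structure and function and treatment response in each arm separately". The 0.58 comes from a published study of inter-hemispheric functional connectivity in 25 patients. The section bases its power on 40 patients in each arm before 20% attrition, and claims more than 90%. The test level is 2.5%, and the reason it gives for that level is this: "as we have 2 correlations the significance level is adjusted".

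**The concern.** A right-IPS value is on the lesion side in a right-hemisphere stroke and on the opposite side in a left-hemisphere stroke. A left-IPS value is the reverse. If response depends on the state of the IPS and its tracts on the damaged side, neither column measures that quantity in all patients. Two things follow for measures taken from one seed.

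- **Dilution.** The pooled correlation averages the ipsilesional and contralesional associations, so a real association is weakened.
- **Confounding.** Stroke side is encoded in the predictor whenever ipsilesional and contralesional values differ on average. If left and right strokes also recover differently, an IPS correlation can arise from side alone. Lesion volume does not remove this. The IPS factor used in randomisation is bilateral preservation, yes or no, so it does not handle side either.

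At stake are objective 3(c), objective 3(b) so far as it uses single-seed connectivity, and hypothesis 2, that patients with impaired IPS structure or function benefit less. A diluted result could be read as negative, and a confounded one as an effect specific to one hemisphere.

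**Working it through.** **Inputs from Protocol 5.7.** 40 per arm including 20% attrition, so 40 × 0.8 = 32 evaluable; r = 0.58; 2.5% level. Sidedness is not stated; two-sided is assumed.

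**The plan's own figure.** With Fisher's z, power = Φ(atanh(r)·√(n−3) − z₀.₉₈₇₅).

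- atanh(0.58) = 0.6625, √29 = 5.385, product 3.568.
- 3.568 − 2.241 = 1.326, and Φ(1.326) = 90.8%.
- The n needed for 90% is 32, and 32/0.8 = 40. The stated figure reproduces.
- Partialling out lesion volume replaces √29 by √28 and gives 89.7%, essentially the same.

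**Reserve.** The smallest r giving 90% at n = 32 is tanh((2.241 + 1.282)/5.385) = tanh(0.654) = 0.574, against the assumed 0.58.

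**Effect of mixing sides.** The protocol gives neither the share of right strokes nor a correlation for the contralesional seed, so both are assumed over a range. Take a right-seed measure and let p be the share of patients in whom it is ipsilesional (right strokes). Suppose its correlation with response is 0.58 in those patients and c in the others. With equal means and variances, pooled r = 0.58p + c(1−p). Each cell gives pooled r and power at n = 32, two-sided 2.5%:

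| p | c = 0 | c = 0.3 | c = 0.58 |
|---|---|---|---|
| 0.9 | 0.522, 81.0% | 0.552, 86.5% | 0.58, 90.8% |
| 0.8 | 0.464, 67.9% | 0.524, 81.4% | 0.58, 90.8% |
| 0.7 | 0.406, 53.1% | 0.496, 75.4% | 0.58, 90.8% |
| 0.6 | 0.348, 38.8% | 0.468, 68.8% | 0.58, 90.8% |
| 0.5 | 0.290, 26.3% | 0.440, 61.9% | 0.58, 90.8% |

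Example for p = 0.8, c = 0.3: 0.8 × 0.58 + 0.2 × 0.3 = 0.524.

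For a left-seed measure, p is the share of left strokes.

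**Mean difference between sides.** If both sides carry r = 0.58 but ipsilesional and contralesional values differ in mean by 1 SD, pooled r = 0.58/√(1 + p(1−p)). At p = 0.5 this is 0.58/√1.25 = 0.519, power 80.3%. At p = 0.9 it is 0.58/√1.09 = 0.556, power 87.1%.

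**Not modelled.** Bilateral strokes, the loss of lesioned seeds, and the size of the confounding. The last would need a recovery difference by side, which the protocol does not give.

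**Which measures are exposed.** FA of tracts from one seed, and connectivity of one seed with the rest of the brain, depend on which side was hit. A correlation between the left and right IPS is the same quantity whichever hemisphere carries the stroke, and is not exposed.

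**The case against.** The strongest reply is that the power statement is anchored to the measure least open to the criticism. The functional predictor in 5.10.4.1 and the source of r = 0.58 are both inter-hemispheric, and the background turns to that measure straight after mentioning the damaged hemisphere. This stands. A reader might infer that every IPS predictor mixes a damaged with a healthy hemisphere and that the stated power is not delivered. The documents do not support that: the power reproduces, the homotopic left-right part of the functional measure does not depend on stroke side, and the losses above rest on assumed inputs. Only the rest-of-brain reading of the functional predictor is exposed.

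Second, lesioned seeds are excluded, so what is mixed is structurally spared ipsilesional seeds with contralesional ones. That is right, but it is no cure. In the right-seed column, exclusions arise only in right or bilateral strokes, so the rule raises the contralesional share of that column and lowers its n.

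Third, anatomical coding is defensible, since part of the background is specific to right-hemisphere structures. This is a reason to keep left and right in the report, not to leave stroke side out of the model.

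Fourth, coding and covariates may be settled in a statistical analysis plan that is not shown. Both seeds and a lesion map will exist, so either coding remains possible. That tempers the point. But the left and right labels stand in the protocol's objectives, and lesion volume is the adjustment it names. The protocol also plans lesion-symptom mapping, but that tests lesion location, not connectivity.

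**Conclusion.** The concern holds for side-specific IPS measures: FA from the left or right seed, and any single-seed-to-rest-of-brain connectivity. As written, each such measure is ipsilesional in some patients and contralesional in others, and is tied to stroke side without adjustment.

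The power above 90% is right for its inputs and for a side-symmetric measure. It is not assured for a side-specific one. Over assumed right-stroke shares of 50% to 90%, the loss runs from none (both sides equally informative, equal means) to a fall to 26.3% (contralesional seed uninformative, half the strokes on each side). No single corrected power can be derived, because the side mix and the contralesional correlation are not in the documents. These calculations also borrow 0.58 as the ipsilesional correlation, for which the protocol gives no evidence.

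Section 5.7 words its power for IPS structure as well as function, although its only source is the inter-hemispheric functional measure. That extension is unsupported.

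**What to change.** In 5.10.4.1, add stroke side as a covariate in the models of side-specific IPS measures. Code those measures as ipsilesional and contralesional from the lesion map that is already planned, state a rule for bilateral strokes, and report this alongside anatomical left and right. Both steps are needed. The covariate removes a mean difference between left and right strokes, but not the dilution from averaging unlike associations. Recoding deals with the dilution, but not with a recovery difference by hemisphere.

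In 5.7, state that the power applies to the inter-hemispheric functional measure from which 0.58 was taken. Do not transfer it to an ipsilesional or FA measure.

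No new data are needed. The cost is one degree of freedom (two if bilateral strokes form their own level) and a few extra reported analyses.

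### As written, no analysis that keeps patients with a lesioned IPS clearly tests whether IPS damage changes the benefit of SIGHT over TAU, which is what hypothesis 2 claims

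*Protocol*

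**What the plan says.** - **Hypothesis.** Protocol 4.2 states that "patients with impaired IPS structure or function will benefit less from SIGHT". Section 4.1 words it a little more widely, adding damage to the projections of the IPS.
- **Seed rule.** Section 5.5.2.2 places a spherical seed in the left and the right IPS of each scanned patient, then says "ROIs overlapping with lesion will be excluded from analysis".
- **Connectivity analysis.** Section 5.10.4.1 correlates the structural and functional measures built on these seeds with the change from baseline to T1, regressing out lesion volume. For the study of the IPS it promises tests within each arm and a test of interaction between arms.
- **Lesion mapping.** The same section assigns lesion location to hypothesis 2 and asks whether particular lesion sites go with smaller change scores. No arm comparison is stated for this part. Section 5.5.2.2 plans the mapping for the full sample of 206.
- **IPS status.** Preservation of the IPS (yes/no), read from routine clinical imaging, is a balancing factor at randomisation, included for the sake of the mechanistic analysis (4.3, 5.9.1.1). It is recorded for every participant before randomisation (5.3.2.3).
- **Sample size.** Section 5.7 takes "a sample of 40 per group, which includes 20% attrition", which "will provide greater than 90% power at 2.5% level of significance" "to detect a correlation of 0.58 between IPS structure and function and treatment response in each arm separately".

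**The concern.** Hypothesis 2 is a statement about effect modification: the difference between SIGHT plus TAU and TAU alone should be smaller when the IPS is impaired. Testing it needs patients with and without impairment, in both arms, and a comparison of the treatment effect between them. The plan splits these requirements over two analyses. The one with a stated arm interaction loses the value for every lesioned seed. The one that keeps patients with lesioned seeds has no stated arm interaction.

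Two misreadings could follow. A null connectivity result might be taken as evidence against hypothesis 2, although it would speak mainly to unlesioned seeds. A lesion-mapping result might be taken as evidence for it, although IPS damage could simply mark slower recovery in either arm. The protocol itself says that some lesion locations go with poor neglect recovery in general (4.1) and that natural improvement is expected in both groups (5.7).

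A smaller concern is that the imaging sample is sized to the bare minimum, with nothing set aside for seeds the plan already intends to exclude.

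**Working it through.** **1. Which analysis tests what**

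| Analysis | Patients with a lesioned IPS | Arm interaction stated? |
|---|---|---|
| IPS connectivity (MRI subset, target 80) | lesioned seed excluded | yes |
| Lesion-symptom mapping (planned for 206) | included | no |
| Main efficacy model | included | no; randomisation factors enter as adjustment only |

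No row has both properties. IPS preservation is not among the baseline variables that 5.10.4.1 lists as possible modifiers.

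**2. The protocol's own power figure**

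Inputs from 5.7: r = 0.58, alpha 0.025, 40 per arm, 20% attrition. Sidedness is not stated; two-sided is assumed because it returns the protocol's 40.

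- Required n = ((2.241 + 1.282) / atanh(0.58))² + 3, with atanh(0.58) = 0.6625. This gives 31.3, so 32 evaluable, and 32 / 0.8 = 40 per arm.
- Power at 32 = Φ(0.6625 × √29 − 2.241) = Φ(1.326) = 90.8%.

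The stated "greater than 90% power" is reproduced. Regressing out lesion volume, as planned, changes √(n − 3) to √(n − 4), and power at 32 becomes 89.7%.

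**3. Power if seeds are lost**

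The overlap rate is not given. The losses below are assumptions, applied to 32 and rounded down, and they take each excluded seed to cost one patient.

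| Loss | Evaluable per arm | Fisher z | Fisher z, lesion volume regressed out |
|---|---|---|---|
| none | 32 | 90.8% | 89.7% |
| 1 patient | 31 | 89.7% | 88.5% |
| 5% | 30 | 88.5% | 87.2% |
| 3 patients | 29 | 87.2% | 85.8% |
| 10% | 28 | 85.8% | 84.2% |
| 20% | 25 | 80.7% | 78.7% |
| 30% | 22 | 74.1% | 71.5% |

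A simulation of the t-test of r under bivariate normality (400,000 draws) gives 91.6% at 32 and 90.6% at 31. With lesion volume partialled out the figures are 90.5% and 89.5%.

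**4. Precision of the missing interaction**

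Inputs: SD 12 and 103 per arm with 20% dropout (5.7), so about 82 per arm; p, the share with an IPS lesion, is assumed to be 20% or 30%.

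SE = 12 × √(2 × [1/(82p) + 1/(82(1 − p))])

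- p = 0.2: SE = 4.69; 95% half-width 1.96 × 4.69 = 9.2 points.
- p = 0.3: SE = 4.09; 95% half-width 1.96 × 4.09 = 8.0 points.

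**The case against.** Several points on the other side stand.

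- **The rule removes seeds, not patients.** A reader might infer that everyone with an IPS lesion leaves the connectivity analysis. The protocol does not say so. A patient with a one-sided lesion may still contribute the other seed, at least to the structural measure, and patients with damaged tracts or disturbed function around an unlesioned seed stay in. How the left-right functional measure is formed when one seed is missing is not stated, and that detail may fairly be left to the SAP.
- **Hypothesis 2 does not rest on connectivity alone.** Lesion mapping is assigned to it in the full sample. This answers a claim that such patients are ignored, but it does not supply the missing comparison of arms.
- **The exclusion is defensible.** A seed inside infarcted tissue gives no valid signal, so it is not simply a low connectivity value.
- **The power loss may be trivial.** A reader might infer that one lost patient per arm breaks the power claim. By Fisher z it moves power from 90.8% to 89.7%, about one point, and the simulated t-test without a covariate stays at 90.6%. The IPS is described as intact in most neglect cases (4.1). About 112 participants are expected to be able and willing to have MRI, against 80 needed. If all were scanned, which is not committed, 56 per arm less 20% attrition and a further 20% seed loss would leave about 35 (56 × 0.8 × 0.8 = 35.8), above the 32 required.
- **A weaker true correlation is not shown.** It is tempting to say that range restriction pulls r below 0.58. That depends on how the cited imaging study treated lesioned seeds, which the protocol does not say. Nor does making IPS lesion a balancing factor show that it is common; the stated reason is balance for the mechanistic analysis.
- **The proposed interaction is imprecise.** Its half-width exceeds the 6.1-point difference the trial is sized to detect. This is true, and it limits the interaction to an estimate.

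**Conclusion.** The point holds as a gap between hypothesis and analysis. The stated arm interaction belongs to an analysis that drops lesioned seeds, and the analysis that keeps those patients has no stated arm interaction. The structural part of hypothesis 2 is therefore not clearly tested as a modification of the treatment effect. This follows from the protocol's text and needs no assumption about how common IPS lesions are. The SAP is not at hand and may add the comparison; the protocol as written does not contain it.

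The power point is secondary. The stated figure is correct at 32 evaluable patients, but there is no stated allowance for excluded seeds. The shortfall is material only if about three or more patients per arm lose their value (87.2% at 29 by Fisher z, 85.8% with lesion volume regressed out). Whether that happens depends on an overlap rate and on a rule for missing seeds that the protocol does not give.

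**What to change.** 1. Add to 5.10.4.1 a treatment-by-IPS-preserved (yes/no) interaction on T1 Star Cancellation in all randomised participants, using the recorded randomisation factor. Report the estimate with its 95% CI and describe it as an estimate, not a powered test. The factor is read from routine imaging and is not identical to overlap with a seed sphere; say so.
2. Keep the seed exclusion. State that connectivity results apply to unlesioned IPS seeds and report the number of seeds and patients excluded by arm.
3. State that lesion mapping of change scores describes recovery and does not by itself show reduced benefit of SIGHT over TAU.
4. In 5.7, say whether the 20% attrition is meant to cover excluded seeds, and restate power at the analysable n.

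The cost is one model on data already collected, plus wording. The downside is imprecision: about ±8 to 9 points under the assumed 20 to 30% prevalence, so a wide interval must not be read as absence of modification.
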